This is a multicentre, open-label phase II study of CFI-400945 and durvalumab in patients with advanced or metastatic triple negative breast cancer. Up to 28 patients will be enrolled. This study is being conducted by the Canadian Cancer Trials Group (CCTG) and supported by AstraZeneca and University Health Network (provision of CFI-400945 only).

1.0 OBJECTIVES

1.1 Primary Objective

To evaluate the objective response rate (RECIST 1.1) of CFI-400945 given with durvalumab.

1.2 Secondary Objectives

- To evaluate Disease Control Rate (DCR, defined as CR or PR or stable disease (SD) > 16 weeks in duration) of CFI-400945 given with durvalumab.
- To evaluate the immune-related response rate (iRECIST) of CFI-400945 given with durvalumab.
- To establish the safety and tolerability of CFI-400945 given orally in combination with durvalumab in a q4w schedule and to confirm the recommended phase II dose (RP2D) in patients with metastatic triple negative breast cancer (TNBC).

1.3 Tertiary Objective

- To assess the pharmacodynamic and immune effects of CFI-400945+durvalumab.

2.0 BACKGROUND INFORMATION AND RATIONALE

Recent advancements in the treatment of breast cancer have led to higher rates of cure for early stage disease, and longer survival for those living with metastatic disease. However, there remains a critical need for new and effective therapies for those whose disease is resistant or becomes resistant to currently available options. This need is especially urgent for triple negative breast cancer (TNBC), an aggressive subtype associated with early lethality, for which chemotherapy is the only approved treatment (apart from PARP inhibitors in patients with germline BRCA1/2 mutations).

Studies of anti-PD-1/PD-L1 immune checkpoint inhibitors have shown some monotherapy activity in TNBC, but this is very limited in patients with features of aggressive disease (liver metastases, elevated LDH), and response rates observed in the second line or later setting are ~ 5%. [Adams 2017(a); Adams 2017(b); Emens 2018].

More recently, multiple clinical trials in the neoadjuvant and metastatic settings have evaluated anti-PD-1/PD-L1 antibodies in combination with cytotoxic chemotherapy in TNBC. The first of these to be reported has shown an improvement in progression free survival with the addition of the anti-PD-L1 antibody atezolizumab to nab-paclitaxel chemotherapy. However, since the majority of patients developing metastatic TNBC have received anthracyclines and taxanes in the neo/adjuvant setting, chemoresistance is a major challenge. Thus, non-chemotherapy options could have significant advantages, both in terms of efficacy and treatment-associated toxicity. This study seeks to augment the efficacy of PD-L1 blockade in TNBC by developing a combination of durvalumab with a first in class inhibitor of Polo-like Kinase 4 (PLK4), a cytotoxic small molecule oral therapy with potent pre-clinical activity in TNBC models which can be safely administered to patients with advanced solid tumours [Mason 2014].

3.0 BACKGROUND THERAPEUTIC INFORMATION

3.1 CFI-400945

Consult the most recent version of the investigator brochure for current information.

3.1.1 Mechanism of Action

In pre-clinical studies, CFI-400945 was shown to be a selective and potent inhibitor of Polo-like Kinase 4 (PLK4), which regulates centriole duplication. CFI-400945 does not inhibit PLK 1-3 at relevant doses. PLK4 is overexpressed in a variety of solid tumours, and elevated expression is associated with poor clinical outcomes [Hu 2006; Miller 2005; Van de Vijver 2002]. Depletion of PLK4 expression in cancer cells by RNA interference leads to mitotic defects and cell death [Mason 2014]. Thus, pharmacologic inhibition of this target is expected to produce antiproliferative and cytotoxic effects against cancer cells, as has been observed in mechanistic studies with CFI-400945.

3.1.2 Experimental Antitumour Activity

CFI-400945 induces apoptosis and inhibits proliferation of human breast cancer cell lines at nanomolar concentrations. In vivo anti-tumour activity of CFI-400945 has been shown in mice bearing human cancer xenografts of multiple histologies, including robust tumour growth inhibition and durable tumour regression in primary tumour xenografts of breast and ovarian cancer [Mason 2014].

3.1.3 Clinical Trials

Human experience with CFI-400945 consists of a dose-finding phase I study (CFI-400945-CL-001) in which subjects with treatment refractory advanced solid tumours were evaluated. As of December 20, 2017, interim safety data are available for a total of 50 subjects treated in 10 cohorts dosed over the range of 3 – 96 mg/day in 28-day continuous cycles. A RP2D of 64 mg/day for the continuous dosing schedule has been established. DLTs in the 72 mg and 96 mg cohorts included G3 neutropenia in both cohorts, G4 febrile neutropenia in the 64 mg and 96 mg cohorts, and asymptomatic G4 lipase elevation in the 72 mg cohort. The common related AEs ($\geq 10\%$) were fatigue, nausea, decreased appetite, diarrhea, neutrophil count decreased and neutropenia. Two possibly related AEs led to study discontinuation; serum amylase/lipase increase (72 mg/day) and febrile neutropenia (64 mg/day). Dose-limiting toxicity (DLT) occurred in four subjects; these were serum amylase/lipase increase and neutropenia (72 mg/day), and two cases of febrile neutropenia (64 mg/day and 96 mg/day). To add an additional safety margin to mitigate risk of early onset myelosuppression seen in a minority of patients, more intensive hematologic monitoring was added to this period, and a 14 day run in (Cycle 0), consisting of 7 days of CFI-400945 dosing followed by 7 days without CFI-400945 dosing was implemented. No cardiac toxicity was observed in the phase I dose escalation or expansion. Please refer to the most recent version of the Investigator Brochure for full details.

3.1.4 Justification of Dose Selection

In the first in human phase I study of CFI-400945, 64 mg/day was determined to be the RP2D, and was the dose selected for the solid tumour expansion cohort. Because of the occurrence of Grade 4 febrile neutropenia in 1 patient in the expansion cohort (1/7 patients treated at 64 mg/day; occurring in a patient with other disease-related factors that may have increased susceptibility to this event), a 14 day run in consisting of 7 days of daily dosing at 64 mg/day followed by a 7-day rest period with no dosing, was implemented to mitigate the small risk of early onset neutropenia. Antitumour activity was observed in the phase I study at doses as low as 48 mg/day.

On this study, a starting dose of 64mg/ day was used. Of the first 5 patients enrolled, 4 had neutropenia. Of these patients, 2 had grade 4 neutropenia within the first cycle, 1 had grade 4 neutropenia within the second cycle and 1 had grade 3 neutropenia within the second cycle. One patient required hospitalization for febrile neutropenia (and growth factors), while a second patient required prophylactic growth factors. Three patients required dose modifications. The study was placed on temporary hold and a safety review was conducted. Other than the usage of a different lot of CFI-400945, the only apparent correlation with clinical factors was a single patient with disease related hepatic dysfunction at baseline. Based upon those data the trial was reopened at 48 mg/day, with a revised dose modification schema, and provision for escalation in selected patients. Six patients were enrolled at this dose level with 5 requiring a dose modification. As a result, the trial was reopened at 40mg/day. Eight patients were enrolled at this dose level. Of these patients, two had grade 4 neutropenia and one had febrile neutropenia. Five patients required a dose hold related to neutropenia and three required a dose reduction related to the neutropenia. As a result, 32 mg/day has been declared as the recommended phase II dose and a safety cohort of six patients will be enrolled prior to opening accrual to additional centres.

3.1.5 Pharmaceutical Data

Supplied:

Refer to the Pharmacy Manual for most current information.

Stability and Storage:

CFI-400945 tablets will be packaged into high-density polyethylene or polypropylene bottles and sealed with a child-resistant closure. CFI-400945 tablets should be stored at ambient temperature (15-30°C).

Route of Administration:

CFI-400945 is taken orally at least 1 hour before, and 2 hours after, any food.

3.2 Durvalumab

See the current durvalumab product monograph for additional details and the most up to date information.

3.2.1 Name and Chemical Information

Durvalumab is a human monoclonal antibody of the immunoglobulin G1 kappa (IgG1κ) subclass that inhibits binding of programmed cell death ligand (PD-L1) (B7 homolog 1[B7-H1], cluster of differentiation [CD]274) to program cell death 1 (PD-1; CD279) and CD80 (B7-1).

3.2.2 Mechanism of Action

Durvalumab binds with high affinity and specificity to human PD-L1 and blocks its interaction with PD-1 and CD80. In vitro studies demonstrate that durvalumab antagonizes the inhibitory effect of PD-L1 on primary human T cells, resulting in their restored proliferation and release of interferon gamma (IFN- γ).

3.2.3 Clinical Trials

As of the most recent Investigator's Brochure, over 6000 subjects have been enrolled and treated in ongoing durvalumab clinical studies. No studies have been completed or terminated prematurely due to toxicity.

The safety profile of durvalumab as monotherapy and combined with other anticancer agents appears consistent with the pharmacology of the target and other agents in the immune checkpoint inhibitor class. No tumour types appeared to be associated with unique AEs. Immune-related AEs (irAEs), which are important risks of immune checkpoint inhibitors, have been observed with durvalumab and include pneumonitis, hepatitis, diarrhea/colitis and intestinal perforation, endocrinopathies (thyroiditis, hypo and hyperthyroidism, adrenal insufficiency, hypophysitis/hypopituitarism diabetes insipidus and Type 1 diabetes mellitus), nephritis, rash/dermatitis, pancreatitis, myocarditis, myositis/polymyositis and rare/less frequent irAEs including neuromuscular toxicities such as myasthenia gravis and Guillain-Barre syndrome. Other inflammatory responses that are rare with a potential immune-mediated etiology include, but are not limited to, pericarditis, sarcoidosis, uveitis and other events involving the eye (e.g. keratitis and optic neuritis), skin (e.g. scleroderma, vitiligo and pemphigoid), hematological (e.g. hemolytic anemia and immune thrombocytopenic purpura) and rheumatological (e.g. polymyalgia rheumatic and autoimmune arthritis) events, vasculitis, non infectious encephalitis or non infectious meningitis. It is possible that events with an inflammatory or immune mediated mechanism could occur in nearly all organs. Please refer to the most recent version of the Investigator Brochure for incidence.

3.2.4 Justification of Dose Selection

Based on average body weight of 75 kg, a fixed dose of 1500 mg Q4W is planned. Fixed dosing of durvalumab is recommended only for subjects with > 30kg body weight due to endotoxin exposure. Patients with a body weight less than or equal to 30 kg should be dosed using a weight-based (20mg/kg) dosing schedule. This is not expected to be applicable to this trial in an adult patient population.

3.2.5 Pharmaceutical Data

Supplied:

Please see the Pharmacy Manual. Durvalumab will be supplied by AstraZeneca/MedImmune as a 500 mg vial solution for infusion after dilution. The solution contains 50 mg/mL durvalumab. The nominal fill volume is 10.0 mL.

Storage:

Investigational product vials are stored at 2°C to 8°C (36°F to 46°F) and must not be frozen. Drug product should be kept in original packaging until use to prevent prolonged light exposure.

Route of Administration:

Intravenous.

4.0 STUDY POPULATION

This study is designed to include women and minorities as appropriate, but is not designed to measure differences in intervention effects.

4.1 Eligibility Criteria

The eligibility criteria for this study have been carefully considered. Eligibility criteria are standards used to ensure that patients who enter this study are medically appropriate candidates for this therapy and to ensure that the results of this study can be useful for making treatment decisions regarding other patients with similar disease(s).

These eligibility criteria are expected to be followed. Any proposed variance must be discussed with CCTG prior to patient enrollment.

4.1.1 Patients must have histologically and/or cytologically confirmed diagnosis of breast cancer, that is advanced/metastatic or unresectable, for which no curative therapy exists, and be negative for ER, PR and HER2 by ASCO/CAP criteria on the most recent sample. Patients with tumour with either low (< 10%) ER expression who are PR and HER2 negative, or ER and HER2 negative but with low PR (< 10%) may be enrolled after discussion and confirmation with CCTG.

4.1.2 Only female patients will be enrolled.

4.1.3 All patients must have a formalin fixed paraffin embedded tissue block (from primary or metastatic tumour) available and must have provided informed consent for the release of the block (see Section 12.1).

Biopsies are optional but strongly encouraged for patients with accessible disease suitable for biopsy. The timing of tumour biopsies for patients who provide informed consent and are willing is prior to treatment (after enrollment; patients with biopsies within 90 days of enrollment with available blocks do not need re-biopsy), and again in Cycle 3, Day 1-8. An additional biopsy at the time of progression in patients with clinical benefit (see Section 5) is also encouraged. Lesions planned for biopsy must not be the only target lesion.

4.1.4 Presence of clinically and/or radiologically documented disease. All radiology studies must be performed within 21 days prior to enrollment (within 28 days if negative).

All patients must have measurable disease as defined by RECIST 1.1. The criteria for defining measurable disease are as follows:

Chest x-ray	≥ 20 mm
CT scan (with slice thickness of 5 mm)	≥ 10 mm → longest diameter
Physical exam (using calipers)	≥ 10 mm
Lymph nodes by CT scan	≥ 15 mm → measured in short axis

4.1.5 Patients must be ≥ 18 years of age.

4.1.6 Patients must have an ECOG performance status of 0 or 1.

4.1.7 Patients must have a life expectancy of 3 months or longer.

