- 13 In order to evaluate tumour growth rate, if additional imaging was done prior to baseline radiology (done 3-12 weeks prior to Baseline scan), scans should also be evaluated according to RECIST 1.1 criteria and submitted with baseline reports. Note selection of target and/or non-target lesions is based on baseline imaging only. The same lesions (target and/or non-target) selected on baseline imaging should then be assessed on the pre-baseline scans if present.
- 14 To be done every three months until relapse or progression (iCPD), for patients with CR/iCR, PR/iPR, SD/iSD response as defined in Section 8.0. Patients with CR/iCR or PR/iPR or equivocal PD (pseudoprogression)/iUPD should have scans repeated after 4 weeks, but no more than 8 weeks, to confirm response.
- 15 Must be confirmed available prior to enrollment on ALL patients. See Section 12.0 for details.
- 16 After enrollment but before the first dose of study treatment. Please refer to Section 12 and the Correlative Studies Manual for details regarding collection.
- 17 Optional paired biopsies should be obtained after enrollment (unless biopsy with available block within 90 days of enrollment) but prior to first dose and Cycle 3 (D1-8). Biopsies are also strongly recommended in all consenting patients when radiological disease progression on therapy is confirmed among patients who had initial response of CR/iCR, PR/iPR or SD/iSD greater than 4 months. See Section 12.1 for details.

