8.2.3 Target Lesions

When more than one measurable tumour lesion is present at baseline all lesions up to *a maximum of 5 lesions total* (and a maximum of *2 lesions per organ*) representative of all involved organs should be identified as target lesions and will be recorded and measured at baseline. Target lesions should be selected on the basis of their size (lesions with the longest diameter), be representative of all involved organs, but in addition should be those that lend themselves to *reproducible repeated measurements*. Note that pathological nodes must meet the criterion of a short axis of ≥ 15 mm by CT scan and only the *short* axis of these nodes will contribute to the baseline sum. All other pathological nodes (those with short axis ≥ 10 mm but < 15 mm) should be considered non-target lesions. Nodes that have a short axis < 10 mm are considered non- pathological and should not be recorded or followed (see 8.2.4). At baseline, the sum of the target lesions (longest diameter of tumour lesions plus short axis of lymph nodes: overall maximum of 5) is to be recorded.

After baseline, a value should be provided on the CRF for all identified target lesions for each assessment, even if very small. If extremely small and faint lesions cannot be accurately measured but are deemed to be present, a default value of 5 mm may be used. If lesions are too small to measure and indeed are believed to be absent, a default value of 0 mm may be used.

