8.2.5 Response

All patients will have their BEST RESPONSE from the start of study treatment until the end of treatment classified as outlined below:

Complete Response (CR): disappearance of *target* and *non-target* lesions and normalization of tumour markers. Pathological lymph nodes must have short axis measures < 10 mm (Note: continue to record the measurement even if < 10 mm and considered CR). Residual lesions (other than nodes < 10 mm) thought to be non-malignant should be further investigated (by cytology specialized imaging or other techniques as appropriate for individual cases [*Eisenhauer 2009*]) before CR can be accepted. Confirmation of response is required.

Partial Response (PR): at least a 30% decrease in the sum of measures (longest diameter for tumour lesions and short axis measure for nodes) of target lesions, taking as reference the baseline sum of diameters. Non target lesions must be non-PD. Confirmation of response is required.

Stable Disease (SD): Neither sufficient shrinkage to qualify for PR nor sufficient increase to qualify for PD taking as reference the smallest sum of diameters on study.

Progressive Disease (PD): at least a 20% increase in the sum of diameters of measured lesions taking as references the smallest sum of diameters recorded on study (including baseline) AND an absolute increase of ≥ 5 mm. Appearance of new lesions will also constitute progressive disease (including lesions in previously unassessed areas). In exceptional circumstances, unequivocal progression of non-target disease may be accepted as evidence of disease progression, where the overall tumour burden appears to have increased by at least 73% in volume or, in select instances where tumour burden has increased sufficiently to require urgent medical intervention (e.g. radiation for spinal cord compression or drainage of a fluid collection). Modest increases in the size of one or more non-target lesions are NOT considered unequivocal progression. If the evidence of PD is equivocal (target or non-target), treatment may continue until the next assessment, but if confirmed, the earlier date must be used.

Table 1: Integration of Target, non-Target and New Lesions into Response Assessment:

Target Lesions	Non-Target Lesions	New Lesions	Overall Response	Best Response for this Category also Requires
Target lesions ± non target lesions				
CR	CR	No	CR	Normalization of tumour markers, tumour nodes < 10 mm
CR	Non-CR/Non-PD	No	PR	
CR	Not all evaluated	No	PR	

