13.2 Sample Size and Duration of Study

A 2-stage Simon minimax design will be used.

For sample size estimation, a response rate of 0.15 to monotherapy is assumed. The null hypothesis that the true response rate is 15% or less will be tested against a one-sided alternative. In the first stage, 15 patients will be accrued. If 2 or less responses are observed, the study will be stopped. Otherwise, accrual will continue to a total of 28. The null hypothesis will be rejected if 8 or more responses are observed in 28 patients. This design yields a type I error rate of 5% and power of 0.8 when the true response rate is 35%.

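### One of several target lesions may be biopsied after the baseline scan and stays in the RECIST sum, and the plan has no rule for scoring it

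*Combined protocol and SAP*

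**What the plan says.** **Which lesion may be sampled.** Section 4.1.3 allows optional biopsies of accessible disease, with one limit: "Lesions planned for biopsy must not be the only target lesion". Section 12.1 describes the same biopsies and adds no further limit on the lesion.

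**When.** Sections 4.1.4 and 5.0 place baseline imaging before enrollment. Footnote 17 of Section 5.0 says: "Optional paired biopsies should be obtained after enrollment", before the first dose, unless a block from the previous 90 days is available. A second sample is planned for Cycle 3, Day 1 to 8.

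**How the lesion is then scored.** Section 8.2.3 makes all measurable lesions targets, up to five in total and two per organ. It continues: "After baseline, a value should be provided on the CRF for all identified target lesions for each assessment, even if very small". Sections 8.2.3 and 8.6 give 0 mm to a lesion thought to be gone and do not ask why it has gone. Section 8.2.5 defines partial response (PR) as "at least a 30% decrease in the sum of measures" from baseline, with confirmation required.

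**What it feeds.** The primary endpoint in Section 13.1 is the proportion of evaluable patients with a complete response or PR by RECIST 1.1. Section 13.2 stops the trial at 2 or fewer responses in 15 patients and rejects the null at 8 or more in 28. Section 11.2 provides no central radiology review.

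**The concern.** The reference sum is fixed before tissue is taken. If a later biopsy shortens or removes a target lesion, the loss counts as shrinkage from baseline. The confirming scan does not correct this, because removed tissue is still absent. The protocol guards against the problem for a sole target lesion. It does not do so for a patient with two or three targets, where one lesion can still decide the response.

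At stake is a single-arm primary endpoint with small counts. One response can decide whether accrual continues after stage 1 or whether the null is rejected at the end.

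**Working it through.** **1. The plan's own figure.** The null is set out in Section 13.2: "The null hypothesis that the true response rate is 15% or less will be tested against a one-sided alternative". Inputs from the same section: first stage 15, stop at 2 or fewer, total 28, reject at 8 or more, target rate 35%. The probability of rejection at true rate p is

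P(p) = sum over x = 3 to 15 of C(15, x) p^x (1 − p)^(15 − x) × Pr[Bin(13, p) ≥ 8 − x].

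- P(0.15) = 0.0461
- P(0.35) = 0.8027
- Probability of stopping at stage 1 when p = 0.15: 0.604

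The stated 5% and 0.8 are met, and a search over designs returns the same minimax design. The design itself is sound.

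**2. Order of events.** The baseline scan comes first, then enrollment, the first biopsy and the first dose. With 28-day cycles and no delay, Cycle 3 Day 1 is day 2 × 28 + 1 = 57, next to the first 8-week scan. A pre-treatment biopsy can therefore affect every later scan. The Cycle 3 biopsy mainly affects scans after the first, and these still count toward best response.

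**3. How much diameter must be lost.** If a lesion loses d mm from a baseline sum of S mm, the change is −d/S. It meets the PR threshold alone only if d/S ≥ 0.30. The lesion sizes below are illustrations.

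| Baseline targets (mm) | Loss needed for PR | Largest fall from fully removing one smallest lesion |
|---|---|---|
| 10 + 20 | 0.30 × 30 = 9 mm | 10/30 = 33.3% |
| 10 + 10 + 10 | 0.30 × 30 = 9 mm | 10/30 = 33.3% |
| 10 + 20 + 20 | 0.30 × 50 = 15 mm | 10/50 = 20% |
| five of 20 | 0.30 × 100 = 30 mm | 20/100 = 20% |

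In the first two rows nearly the whole 10 mm lesion must go. In the last two, even complete removal of that lesion is not enough without shrinkage elsewhere. A biopsy that takes little tissue comes nowhere near these losses. The exposed case is a small or superficial lesion in a patient with few targets; Section 8.6.1 accepts superficial lesions from 10 mm as measurable.

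**4. Effect of one patient.** One false PR turns 2/15 into 3/15 (stop becomes continue) or 7/28 into 8/28 (not rejected becomes rejected). It adds 1/28 = 3.6 percentage points to the final response rate.

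**5. Sensitivity, by assumption only.** Let q be the share of true non-responders scored as PR because of sampling. The documents give no value for q. At a true rate of 15% the observed rate becomes 0.15 + 0.85q, and the expected number of false PRs in 28 patients is 28 × 0.85 × q = 23.8q.

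| q (assumed) | Expected false PRs | Probability of rejection | Probability of stage 1 stop |
|---|---|---|---|
| 0 | 0 | 0.046 | 0.604 |
| 1% | 0.24 | 0.061 | 0.567 |
| 2% | 0.48 | 0.078 | 0.531 |
| 5% | 1.19 | 0.148 | 0.427 |

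The table shows how sensitive the rule is to any false response. It does not estimate what biopsies would cause.

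**The case against.** The case against has real force.

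- **The text says biopsy, not excision.** Section 12.1 mentions resections only for archival tissue and uses only biopsies for the paired study samples. Technique may also be covered in the separate Correlative Studies Manual, which is not among these documents. This point stands. A reader might infer that study biopsies remove whole lesions, but no section provides for that.
- **Zero is not the only possible score.** The response table in Section 8.2.5 gives a not-evaluable result when target lesions are not all evaluated, and a sampled lesion might be put there. That is possible, but no text directs it, so sites could differ.
- **Partial checks exist.** Section 11.1 has data managers and physicians review source documents, and Appendix IV requires radiology reports and tumour measurement sheets. A response driven by one vanished lesion could be noticed. The reviewer would still have no stated rule to apply.
- **The chain is long.** It needs consent, sampling of a target, large tissue loss, a large enough share of the sum, no progression elsewhere and a confirming scan. Swelling after a biopsy could also push the measurement the other way. So neither the frequency nor the net direction is known.

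These points limit the size of the problem. They do not supply the missing scoring rule.

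**Conclusion.** The gap is in the text: a target lesion can be sampled after baseline, it stays in the sum, and Section 8 does not say how to treat it. For a small-volume biopsy the effect is close to nil. A PR caused by sampling alone requires loss of at least 30% of the baseline sum from the sampled lesion; smaller losses can only add to real shrinkage. How often either would occur cannot be worked out from the documents, which give neither biopsy technique nor uptake.

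Two stronger readings are tempting, and the documents support neither. One is that the type I error is inflated to some definite figure above 5%: the rates in the sensitivity table rest wholly on an assumed q. The other is that any PR depending on a sampled lesion should be refused: that could discard true responses and bias the response rate downward.

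What remains is a cheap improvement, worth making because a single patient can change the decision at either boundary.

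**What to change.** 1. In Sections 4.1.3, 8.2.3 and 12.1, state that for patients enrolled from now on a lesion planned for biopsy should not be selected as a target when another measurable lesion is available. Mark this in 8.2.3 as an exception to the rule that takes in all measurable lesions up to five. It has to be prospective: Section 3.1.4 already reports 5 + 6 + 8 = 19 patients enrolled.
2. Where a target lesion is sampled, record the lesion, date and technique on the tumour measurement sheet, including for patients already enrolled.
3. In Section 13.1, add a sensitivity analysis of the response rate that leaves sampled lesions out of both the baseline and the follow-up sums. Report whether the 8-of-28 decision changes.

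The cost is a few sentences, one entry on an existing form and one extra tabulation. A few patients will have one fewer target lesion. The primary analysis, sample size and decision rule do not change. These rules should be fixed before responses are tabulated, since added later they could look chosen to suit the result.
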